## 7 STUDY INTERVENTION DISCONTINUATION AND PARTICIPANT DISCONTINUATION/WITHDRAWAL

### 7.1 DISCONTINUATION OF STUDY INTERVENTION

Discontinuation from study intervention (anticoagulant use) does not mean discontinuation from the study, and remaining study procedures should be completed as indicated by the study protocol. If a clinically significant finding is identified (including, but not limited to changes from baseline) after enrollment, the investigator or qualified designee will determine if any change in participant management is needed. Any new clinically relevant finding will be reported as an adverse event (AE). Events that may trigger include:

1. Major bleeding event. The anticoagulant will be discontinued and future management of anticoagulant will be decided by the treating physician. The patient will not be re-challenged with anticoagulant as part of the study protocol.
2. Ischemic Stroke / TIA. Management of anticoagulant in the first month following an ischemic stroke / TIA will be determined by the treating physician. Following this, a decision regarding whether to continue study intervention will be made in consultation with the treating physician and the patient. Whether the anticoagulant was being used in a therapeutic fashion at the time of event will be part of this discussion.
3. Hemorrhagic stroke. The study intervention will be discontinued and future anticoagulation decision will be made by the treating physician.
4. Participants will be strongly encouraged by the study staff to remain on treatment assigned through randomization and to comply with the study protocol and follow-up. However, participants or their physician may voluntarily discontinue study intervention or change OAC treatment at any time. Study staff will make every effort to discourage this.

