Participants who change OAC treatment during follow-up will be withdrawn from the study. A CRF will collect details of the reason for discontinuation of study intervention. Endpoints will be assessed at the time of withdrawal from the study including MRI and cognitive function. The MRI of the head and / or cognitive assessment will be performed at the time of withdrawal from the study if it is greater than 6 months since their last assessment of MRI and / or cognitive function. If a patient withdraws within 6 months of the last assessment, repeat testing will not be performed and the last assessment will be used for the analysis. Participants who withdraw from the study will be followed for 30 days after withdrawal for adverse events. A primary intention to treat analysis will be performed at the end of the study. Participants who withdraw or change OAC treatment will be censored at the time of withdrawal.

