### 9.3 POPULATIONS FOR ANALYSES

The following datasets will be used for analysis:

1. Intention-to-Treat (ITT) Analysis Dataset (i.e., all randomized participants)
2. Per-Protocol Analysis Dataset: defines a subset of the participants in the full analysis set who complied with the protocol sufficiently to ensure that these data would be likely to represent the effects of study intervention according to the underlying scientific model.
3. Pre-specified subgroup analyses – (1) Gender, (2) decade of age, (3) pattern of AF, (4) warfarin naïve vs prior warfarin exposure, (5) Time in therapeutic range on warfarin divided by the median.

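### Section 7.1 withdraws and censors everyone who changes anticoagulant, so the treatment-policy effect behind its primary intention-to-treat analysis cannot be estimated from observed data

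*Combined protocol and SAP*

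**What the plan says.** Section 7.1 opens with one rule: "Discontinuation from study intervention (anticoagulant use) does not mean discontinuation from the study, and remaining study procedures should be completed". It accepts that "participants or their physician may voluntarily discontinue study intervention or change OAC treatment at any time". It then sets a different rule for changes of drug: "Participants who change OAC treatment during follow-up will be withdrawn from the study", and "Participants who withdraw or change OAC treatment will be censored at the time of withdrawal". Between those two sentences stands "A primary intention to treat analysis will be performed at the end of the study". Section 9.3 lists the "Intention-to-Treat (ITT) Analysis Dataset (i.e., all randomized participants").

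On data after a change, section 7.1 says an exit MRI or cognitive assessment "will be performed at the time of withdrawal from the study if it is greater than 6 months since their last assessment"; otherwise the last assessment is used. After that, "Participants who withdraw from the study will be followed for 30 days after withdrawal for adverse events".

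Four other places bear on this:
- Section 7.2 lets an investigator withdraw a participant for significant non-compliance, and lets people who were randomized but never treated be replaced.
- Section 8.1 (brain MRI) plans an attempt at MRI before any early withdrawal, with no 6-month condition.
- Section 9.1 censors people who stop in-person testing from the primary endpoint.
- Section 9.4.1 specifies linear mixed effects models, but no missing-data strategy and no estimand for a change of treatment.

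**The concern.** The intention-to-treat effect is the effect of assignment whatever treatment was taken later, so it needs outcomes after the change. The plan stops collecting them. The primary result would carry the intention-to-treat label but answer another question, and scores that were never taken cannot be recovered at analysis.

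The rule also splits similar participants. Someone who stops the study drug without changing to another anticoagulant stays in, unless withdrawn under section 7.2. Someone who changes drug must leave. Treatment is open label (section 6.3) and changes are at the participant's or physician's discretion, so leaving may be related to prognosis and may differ by arm.

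**Working it through.** **1. What is observed after a change.** Assume the change falls uniformly over 0-24 months; the documents give no timing.

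| Month of change | Exit cognitive test | Scheduled cognitive tests lost |
|---|---|---|
| 0-6 | no | 1-year, 2-year |
| 6-12 | yes | 1-year, 2-year |
| 12-18 | no | 2-year |
| 18-24 | yes | 2-year |

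- Scheduled tests lost per switcher: 0.5 x 2 + 0.5 x 1 = 1.5.
- Exit tests gained per switcher: 0.5. Net loss: 1.5 - 0.5 = 1.0.
- The first row, 25% of switchers, has no post-baseline score.
- Every switcher loses the 2-year MRI. Section 7.1 gives those in the first row no exit MRI either; section 8.1 says one will be attempted.

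For scale, take assumed switching of 20% on warfarin and 5% on apixaban with 140 per arm: 28 + 7 = 35 people. The gross loss is 35 x 1.5 = 52.5 of 560 follow-up tests (9%). The net loss is 35 of 560 (6%).

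**2. What the model then estimates.** With scores only up to the change, the mixed model extrapolates each switcher's course on the assigned drug. Under missing at random this is a no-switch effect. If 20% of the warfarin arm crosses to apixaban at 1 year on average and takes the apixaban slope from then on, the effect of assignment is 0.05 x (1 - 0.20 x 0.5) = 0.045/year. The no-switch target stays at 0.05/year.

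**3. The plan's power, then power with crossover.** Section 9.2 gives a difference of 0.05/year, SD 0.16, one-sided alpha 0.05 and 140 per arm. Power = Phi(d / (0.16 x sqrt(2/140)) - 1.645).
- d = 0.05: 0.834, which reproduces the stated figure of more than 80% (127 per arm would give 80%).
- d = 0.045 (20% of warfarin crosses over): 0.761; 157 per arm for 80%.
- d = 0.05 x (1 - 0.25 x 0.5) = 0.04375 (5% of apixaban also crosses): 0.740; 166 per arm for 80%.

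The present plan also loses information. In the worst case, where the 20% of warfarin switchers contribute no slope, 112 remain against 140. The standard error is 0.16 x sqrt(1/112 + 1/140) = 0.0203, and power for 0.05 is Phi(0.05/0.0203 - 1.645) = 0.79. Section 9.2 inflates 140 to 175 for screen failure only.

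**4. Bias of the no-switch estimate if switching is informative.** The planned mixed model was simulated with visits at 0, 1 and 2 years and the exit-test rule of section 7.1. There was no true treatment effect. Slope and residual SDs were 0.10/0.177 or 0.14/0.11, each matching the per-person slope SD of 0.16. The intercept SD of 0.8, uniform timing and a 0.10/year faster decline in switchers are all assumed. Bias is the censored minus the full-follow-up estimate, in absolute value per year:
- 2.5% warfarin, 1.7% apixaban: 0.0004-0.0005 (about 1% of 0.05).
- 20% warfarin, 5% apixaban: 0.0072-0.0093 (14-19%).
- 20% in both arms, same excess: 0.0000.
- 20% in both arms, only warfarin switchers declining faster: 0.0094-0.0120 (19-24%).

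This measures failure of missing at random. It is separate from the gap between estimands in step 2.

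**The case against.** The best defence is that an all-randomized dataset, which is all section 9.3 asks for, can still be formed. Every randomized person enters the mixed model with scores up to withdrawal, and half of switchers (under uniform timing) have an exit test. That stands. A reader might infer that no intention-to-treat analysis can be produced at all; the documents do not support that. What is lost is the treatment-policy effect from observed data.

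A reader might also infer a known bias, perhaps against apixaban. Section 2.3.1 reports more bleeding discontinuation on warfarin in the cited pivotal trial (2.5% against 1.7%), and the study pays for apixaban but not warfarin. This does not carry the inference. Those percentages are discontinuations for bleeding, not changes of anticoagulant. No passage says that switchers decline faster. Prior warfarin users are eligible and, if assigned apixaban, could go back. The assumed 0.10/year excess is also large: twice the planned effect.

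Finally, the exit MRI planned in section 8.1 softens the imaging loss. It is still not a 2-year MRI, and the two sections disagree on when it is done.

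**Conclusion.** The point holds. Within section 7.1, the withdrawal and censoring rule contradicts both the opening rule on stopping treatment and the named primary analysis, and no other section restores the missing 1- and 2-year outcomes. Followed as written, the plan reports as intention to treat an estimate that is at best a no-switch effect under missing at random. Censoring is also undefined for a mixed model of scores. The replacement rule in section 7.2 adds a second conflict if replaced participants are dropped from the all-randomized set.

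This must be fixed, because the loss is irreversible once follow-up ends. That conclusion needs no predicted bias: with no documented switching rate, the bias could be negligible or around a fifth of the planned effect, in either direction. The lost-test counts rest on uniform timing.

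**What to change.** Reconcile sections 7.1, 7.2, 8.1 (brain MRI), 9.1 and 9.3 as follows:
- Delete withdrawal from the study and censoring for a change of anticoagulant.
- Keep the scheduled 1- and 2-year cognitive tests and 2-year MRI for every randomized participant who has not withdrawn consent.
- Analyse all these data by assigned arm in the primary mixed model. State that earlier scores of people who stop attending stay in, and that replaced participants remain in the intention-to-treat set.
- Move censoring at a change of anticoagulant to the per-protocol analysis or a sensitivity analysis, labelled as a no-switch effect under missing at random.
- Set one rule for the exit MRI.
- State the expected switching rate and the resulting power in section 9.2.

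The cost is wording, plus testing switchers at visits already on the schedule. Crossover dilutes the effect: at the assumed 20% on warfarin, power is 0.76 rather than 0.83, and 80% would need 157 per arm. Set against the present plan with the same switching (0.79 at worst), the drop is smaller. Management of anticoagulation is untouched.

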### 7.2 PARTICIPANT DISCONTINUATION/WITHDRAWAL FROM THE STUDY

Participants are free to withdraw from participation in the study at any time upon request.

An investigator may discontinue or withdraw a participant from the study for the following reasons:

- Significant study intervention non-compliance
- If any clinical adverse event (AE), laboratory abnormality, or other medical condition or situation occurs such that continued participation in the study would not be in the best interest of the participant
- If the participant meets an exclusion criterion (either newly developed or not previously recognized) that precludes further study participation.

The reason for participant discontinuation or withdrawal from the study will be recorded on the Case Report Form (CRF). Subjects who sign the informed consent form and are randomized but do not receive the study intervention may be replaced.

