### *Role of Anticoagulation*

The central role of cerebral infarctions and CMBs in the association between AF and dementia suggests that anticoagulation could be a key player in the association. It is plausible that effective anticoagulation of AF-patients could reduce the risk of cognitive impairment by reducing the risk of cerebral infarction. Anticoagulation however also increases the risk for macro- and micro- bleeds in the brain, which in turn may increase the risk of cognitive dysfunction. Hence an ideal anticoagulant should reduce the incidence of cerebral infarcts without significantly increasing the risk of cerebral hemorrhage.

Some observational studies have investigated the impact of various anticoagulation strategies for AF treatment on dementia. Warfarin, as the most common prescribed anticoagulant, was the initial focus of many studies and it was shown that warfarin could reduce the incidence of dementia in patients with AF. However, it has a narrow therapeutic window and its efficacy in reducing dementia is contingent on maintaining a high time in therapeutic range; rates of incident dementia were nearly 2-fold higher in the subjects with the poorest anticoagulation maintenance compared to those with the highest anticoagulation time in therapeutic range. We also recently published further supporting evidence with the addition that supra-therapeutic INRs on warfarin increase the risk for dementia compared to therapeutic INR. While sub-therapeutic INR increases risk of cerebral embolism, supra-therapeutic INR can increase cerebral microbleeds and intracranial hemorrhage. Patients with an INR>3 more than 25% of the time are 2.4 times more likely to develop dementia. While supratherapeutic INR is a risk for CMB, it has also been highlighted that patients in general who are treated with vitamin K antagonists (VKA) were more likely to have CMBs. Hence it is becoming increasingly clear that warfarin may not be the ideal anticoagulant to prevent the devastating complication of cognitive impairment.

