### 6.3 MEASURES TO MINIMIZE BIAS: RANDOMIZATION AND BLINDING

Study participants will be randomized 1:1 to either Apixaban or dose adjusted Warfarin. Placebo pills will not be administered. Participants, the principal investigator and study coordinator will not be blinded to treatment assignment. Study personnel administering and interpreting the MRI images and cognitive function assessment will be blinded to treatment assignment. Randomization codes will be generated at the time of enrollment and each individual's cognitive function tests and MRI scan identified by this code. Blinding of participants in this study will require the use of placebo and INR testing in both groups, which will be burdensome to the patient and will not affect the outcomes of cognitive function or MRI findings.

Unblinding of personnel to treatment assignment will be performed only when there is a serious adverse event such as intra-cranial hemorrhage.

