#### **Interview by study coordinator**

Interview of the subject by study coordinator at 1- and 2- year follow-up to assess (1) new medical conditions, (2) adverse events, (3) continued eligibility for the study, (4) medication compliance and (5) review of co-administered medications.

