### 9.4 STATISTICAL ANALYSES

#### 9.4.1 GENERAL APPROACH

Continuous and categorical variables will be summarized as mean (standard deviation, SD) and number (%) respectively. Differences between the two treatment arms at baseline will be examined using t-tests for continuous variables and chi-square tests for categorical variables.

The baseline variables include age, sex, education, cardiovascular risk factors (hypertension, diabetes mellitus, hyperlipidemia), past medical history (including stroke, TIA, heart failure, peripheral arterial disease, MI, coronary artery disease, liver disease, renal disease, malignancy), duration of AF, pattern of AF (paroxysmal, persistent), prior h/o anticoagulation (duration and type of drug used), prior treatment of AF (antiarrhythmic drug, ablation procedure), and current medications. This data will be reviewed and updated at each visit. The INR values during the study will be collected for patients on warfarin and the time in therapeutic range calculated using the Rosendaal method of interpolation.

Longitudinal changes in each cognitive domain (language, attention, memory, visual spatial and global) will be analyzed using multiple adjusted linear mixed effects models comparing Apixaban vs warfarin. These models will be adjusted for baseline variables that differ between the groups. These results will be presented as beta estimates for baseline differences in cognitive function score by treatment status, change with time and the effect of treatment on the change in scores over time.

For the secondary end point of dementia/MCI, the mid-point between the most recent visit with a cognitively normal diagnosis and the first visit with a diagnosis of MCI or dementia will be considered the date of onset. Participants who are lost to follow-up or die during follow-up will be censored at the

date of last follow-up. Cox proportional hazards model will be used to assess the secondary end points of MCI/dementia, cerebral infarction and cerebral microbleeds. Adjustment for baseline factors noted above will be performed in the multivariable model.

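### Section 7.2 lets an investigator withdraw participants from the study for undefined non-compliance, and they are then censored; this conflicts with Section 7.1 and the intention-to-treat analysis, and the loss could differ by arm

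*Combined protocol and SAP*

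**What the plan says.** Section 7.2 states that "An investigator may discontinue or withdraw a participant from the study for the following reasons", and the first reason listed is "Significant study intervention non-compliance". No degree, duration or method of measurement is given, and nothing says that the standard is the same in both arms.

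Section 7.1 opens with the contrary principle: "Discontinuation from study intervention (anticoagulant use) does not mean discontinuation from the study, and remaining study procedures should be completed". Its closing paragraph then withdraws anyone who changes oral anticoagulant, promises a primary intention-to-treat analysis, and censors those who withdraw at the time they leave. Section 9.3 defines the intention-to-treat set as all randomised participants and also provides a per-protocol set.

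On who knows what, Section 6.3 says: "Participants, the principal investigator and study coordinator will not be blinded to treatment assignment". Section 9.4.1 says: "The INR values during the study will be collected for patients on warfarin", from which time in therapeutic range is calculated. Section 6.2 has apixaban mailed every 6 months and describes no pill count or return of unused drug. The compliance check common to both arms in Section 8.1 is an "Interview of the subject by study coordinator at 1- and 2- year follow-up".

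**The concern.** Adherence is an outcome of randomised treatment. Ending follow-up because of it makes membership of the primary comparison depend on something that happens after randomisation. Here the decision is discretionary and the criterion undefined, and the principal investigator is unblinded. The evidence on exposure also differs between arms: a series of laboratory values for warfarin, mainly self-report for apixaban. Withdrawal could therefore occur at different rates, and in different kinds of patient, in the two arms.

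Prognosis may be involved. Section 2.2 reports that "rates of incident dementia were nearly 2-fold higher in the subjects with the poorest anticoagulation maintenance". If patients withdrawn for non-compliance differ in cognitive decline from those who stay, the estimated difference in slopes no longer describes everyone randomised. The model in Section 9.4.1 adjusts for baseline variables that differ between groups. It can allow for withdrawal driven by later adherence only through scores already observed.

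**Working it through.** **1. The rules side by side.** A patient who stops the anticoagulant altogether stays in the study under the opening of Section 7.1. A patient who takes it irregularly may be removed from the study under Section 7.2 and censored under the end of Section 7.1. Both belong to the intention-to-treat set of Section 9.3. These rules cannot all be followed as written.

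**2. What data are lost.** Section 7.1 provides exit cognitive testing and MRI when more than 6 months have passed since the last assessment of each; otherwise the last assessment is used. By time of withdrawal:

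- Within 6 months of baseline: baseline values only, so no information on that patient's slope and no follow-up MRI.
- From 6 months up to the year-1 visit: an exit score and exit MRI, but nothing later.
- Within 6 months after the year-1 visit: two cognitive scores, hence a one-year slope, but no later score. An exit MRI is due.
- Later than that: an exit score and exit MRI.

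The loss is complete for slope only in the first group.

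**3. The plan's own power.** Inputs from Section 9.2: warfarin slope -0.12/year, SD 0.16, difference 0.05/year, 140 per arm, one-sided alpha 0.05. The implied apixaban slope is -0.12 + 0.05 = -0.07.

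- Standard error = 0.16 × √(1/140 + 1/140) = 0.01912
- Power = Φ(0.05/0.01912 − 1.645) = Φ(0.970) = 83.4%, which agrees with the stated figure of more than 80%.
- Accrual: 140/(1 − 0.20) = 175 per arm. This covers screen failure only, so there is no stated allowance for loss after randomisation.

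**4. Illustration of size.** Let a fraction f of the warfarin arm be withdrawn and contribute no data, with mean slope s, and let no one be withdrawn from the apixaban arm. Both f and s are assumptions; the documents give neither.

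- Remaining warfarin slope m = (−0.12 − f·s)/(1 − f)
- Contrast d = −0.07 − m
- Power = Φ(d / [0.16 × √(1/(140(1−f)) + 1/140)] − 1.645)

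| f | warfarin n | s | m | d | power |
|---|---|---|---|---|---|
| 5% | 133 | −0.12 | −0.120 | 0.050 | 82.5% |
| 5% | 133 | −0.18 | −0.117 | 0.047 | 78% |
| 5% | 133 | −0.24 | −0.114 | 0.044 | 73% |
| 10% | 126 | −0.12 | −0.120 | 0.050 | 81.6% |
| 10% | 126 | −0.18 | −0.113 | 0.043 | 71% |
| 10% | 126 | −0.24 | −0.107 | 0.037 | 59% |

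For example, with f = 10% and s = −0.18: m = (−0.12 + 0.018)/0.9 = −0.1133; d = 0.0433; standard error = 0.16 × √(1/126 + 1/140) = 0.01965; power = Φ(2.206 − 1.645) = 71%.

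Losing the patients costs less than 2 percentage points. The rest of the fall comes from the assumed difference in slope.

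**The case against.** A reader might infer that INR exposes non-compliance in the warfarin arm alone, so that poorly controlled warfarin patients are selectively removed and the result is biased toward no difference. The documents do not support this.

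- Compliance is asked about at 1 and 2 years without restriction by arm, and medications are reviewed in both. The arms differ in how objective and frequent the information is.
- Nothing equates an out-of-range INR with non-compliance. The protocol itself names a narrow therapeutic window, diet and interactions as influences on INR. Another ground in Section 7.2 begins "If any clinical adverse event (AE), laboratory abnormality, or other medical condition or situation occurs", but it applies only where continued participation is not in the participant's best interest.
- Section 9.3 plans a subgroup by time in therapeutic range split at the median, so patients with low values are expected in the analysis.
- Section 6.2 leaves INR management to the treating physician or clinic. Nothing says that the investigator reviews INR during the trial to judge adherence.
- Section 7.2 permits withdrawal and does not require it.

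On size, Section 9.2 reports similar decline in AF patients with and without warfarin. On that evidence, under-treated warfarin patients need not decline faster than −0.12/year. The statement in Section 2.2 concerns incident dementia by INR control; it gives no cognitive slope and no effect of non-compliance. Exit testing keeps much of the data, whereas the illustration discards all of it.

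All of this stands, and it limits what can be said about size and direction. It does not answer the undefined criterion, the unblinded discretion, the censoring, or the conflict with the opening of Section 7.1 and with the intention-to-treat set. One further objection is also fair: the rule that withdraws patients who change anticoagulant is mandatory, so correcting Section 7.2 alone would not be enough.

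**Conclusion.** The concern holds as a defect in the withdrawal rule. The plan permits adherence-related loss of randomised participants, by a decision that can be made with knowledge of the arm and on exposure information that differs between arms. It then censors them in an analysis described as intention-to-treat.

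Its effect on the result cannot be determined from the documents. With 10% of the warfarin arm removed, power is about 82% if their slope equals the rest and 71–59% if it is −0.18 to −0.24/year; with 5% removed, the figures are 82.5% and 78–73%. The lower values rest on assumed slopes, on no data from withdrawn patients, and on no matching withdrawals from the apixaban arm, so they are pessimistic illustrations and not forecasts. The direction is also open: withdrawn warfarin patients who declined more slowly than average, or withdrawals from the apixaban arm, could move the contrast the other way. The case for change rests on the conflict between the rules and the low cost of removing it.

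**What to change.** - In Section 7.2, remove non-compliance as a reason to end study follow-up.
- State that non-compliant participants remain in all planned cognitive and MRI assessments and are analysed in the arm assigned, without censoring for non-compliance.
- Let non-compliance affect only membership of the per-protocol set in Section 9.3.
- Report withdrawals by arm and reason.
- Reconcile Section 7.2, and the withdrawal and censoring rule at the end of Section 7.1, with the opening of Section 7.1 and the intention-to-treat definition in Section 9.3.

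The cost is a change of protocol wording and a few more assessments, already planned, in non-adherent patients. The change concerns data collection and analysis only; no change to treatment management is proposed.

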#### *Economic*

During the trial the patient will receive Apixaban (if randomized to the Apixaban arm) drug therapy free of charge. Warfarin and its monitoring will not be paid for by the study since it is considered the standard of care. The cost of medical care or other costs related to any adverse events will not be covered by the study. Following completion of an individual's participation in the trial (due to end of follow-up, or withdrawal from the study), the cost of all medications and related monitoring will be borne by the patient and/or their insurance – these costs will not be covered by the study.

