## 6.2 PREPARATION/HANDLING/STORAGE/ACCOUNTABILITY

*Apixaban arm:* The drug will be provided by and paid for by BMS / Pfizer. The drug will be provided to Mayo Clinic. It will be distributed to patients once every 6 months via mail by the Mayo Clinic Pharmacy. Apixaban will be stored at 20°C to 25°C (68°F-77°F); excursions permitted between 15°C and 30°C (59°F-86°F) per the drug labeling.

*Warfarin arm:* Warfarin will be prescribed by the treating physician. INR monitoring and dose adjustment will also be performed by the treating physician / assigned anticoagulation clinic. Warfarin will not be provided or paid for by the study.

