## 8 STUDY ASSESSMENTS AND PROCEDURES

### 8.1 EFFICACY ASSESSMENTS

#### **Screening assessment**

Screening for eligible participants will be performed using the Mayo medical records by a study coordinator. Only patients who have previously given consent to the use of their medical records for research purposes will be screened. ECG, Holter, telemetry recordings will be reviewed to confirm the diagnosis of AF. Charts will be reviewed to assess eligibility for the study including past medical history, current medications, laboratory tests and calculation of the CHA2DS2-VaSC score. The creatinine will be checked if a measurement within 3 months of enrollment is not available.

Potential participants will be contacted in person or through a letter or on the phone. Interested persons will be interviewed on the phone to confirm eligibility and will have a blood test for creatinine if needed. Once enrolled, subjects will be randomized to one of the study arms and will start study drug.

Baseline assessment of brain MRI will be performed prior to initiation of study drug. Baseline assessment of cognitive function will be performed prior to or within 1 month of enrollment. Subsequent assessments will be performed at 1 and 2 year follow-up or within a 3 month time frame of this date.

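### Section 7.2 lets randomised non-starters be replaced, and the plan does not reconcile this with a primary ITT analysis of all randomised participants

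*Combined protocol and SAP*

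**What the plan says.** - **Replacement.** Section 7.2: "Subjects who sign the informed consent form and are randomized but do not receive the study intervention may be replaced". It does not say who decides, within what time, which arm or stratum the new patient joins, or what happens to the data of the patient replaced.
- **Analysis set.** Section 9.3 lists the "Intention-to-Treat (ITT) Analysis Dataset (i.e., all randomized participants"), and Section 7.1 makes it primary: "A primary intention to treat analysis will be performed at the end of the study".
- **Leaving or switching.** The next sentence of Section 7.1 reads: "Participants who withdraw or change OAC treatment will be censored at the time of withdrawal". The same section opens by saying that stopping the intervention is not the same as leaving the study.
- **Knowledge of allocation.** Section 6.3: "Participants, the principal investigator and study coordinator will not be blinded to treatment assignment". Section 8.1 (Screening assessment) puts randomisation before drug: "Once enrolled, subjects will be randomized to one of the study arms and will start study drug".
- **Supply.** Apixaban is free to participants. For warfarin, Section 6.2 says "Warfarin will not be provided or paid for by the study", and Section 2.3.1 (Economic) extends this to monitoring.
- **Baseline testing.** Section 8.1 requires the baseline MRI before study drug, but allows the baseline cognitive battery up to one month after enrolment. Section 3 allows it up to one month after randomisation.
- **Sample size.** Section 9.2 raises 140 to 175 per arm for screen failures only. Section 5.4 defines these as people who consent but are not randomised or entered.

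**The concern.** An ITT comparison is protected because group membership is fixed at randomisation. A discretionary rule that takes effect once unblinded staff and patients know the arm can weaken that protection. The people who decline to start may differ in prognosis from those who accept, and they may differ between arms. If they drop out of the analysed data and accepting patients fill their places, the analysis compares two willing subgroups while still being labelled ITT. The mixed model in Section 9.4.1 offers no remedy for a patient without any cognitive score, and a patient with a baseline score only gives no direct information on slope. What is at stake is the primary result, the between-arm difference in the rate of global cognitive decline.

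**Working it through.** **1. The plan's own figure.** Section 9.2 gives a difference of 0.05/year, SD 0.16/year, one-sided alpha 0.05 and 140 per arm.

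- SE = 0.16 × √(2/140) = 0.0191
- Power = Φ(0.05/0.0191 − 1.645) = 83.4% (83.2% by noncentral t)
- Accrual = 140/0.8 = 175 per arm

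Both agree with the plan (more than 80% power; 175 per arm). No stated number is wrong on this point.

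**2. Can the two rules coexist?** Yes, if the replaced patient stays in the ITT set under the assigned arm and the added patient is simply the next randomisation. No section says this, and no section says the opposite.

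**3. Can a non-starter leave the primary analysis in practice?** There are three routes.

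- The cognitive battery may follow randomisation by up to a month, so someone who declines on learning the arm may have no score at all.
- A patient who declines the assigned drug and takes another oral anticoagulant may be treated as having changed treatment, and so be withdrawn and censored under Section 7.1.
- Dementia found at first evaluation is an exclusion (Section 5.2, item 11). With late testing it can surface after randomisation, and Section 7.2 permits withdrawal for an exclusion not previously recognised.

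**4. Size if non-starters are lost.** Let a fraction q of an arm be lost, with slopes steeper by g than those of acceptors. Removing them shifts the arm's mean slope by q × g. The documents give neither quantity, so both are assumptions.

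With q = 10% (warfarin) and 2% (apixaban), and g = 0.05 to 0.10/year in both arms:

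- (0.10 − 0.02) × 0.05 = 0.004/year, and 0.004/0.05 = 8% of the target
- (0.10 − 0.02) × 0.10 = 0.008/year, and 0.008/0.05 = 16% of the target

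In this direction the bias hides an apixaban benefit:

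- Φ((0.05 − 0.004)/0.0191 − 1.645) = about 78% power
- Φ((0.05 − 0.008)/0.0191 − 1.645) = about 71% power

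If non-starters decline more slowly, the sign reverses. One-sided type I error, Φ(bias/0.0191 − 1.645), is then about 7.6% to 11.0% instead of 5%.

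A wider range, with loss in one arm only, bias = q × g, and type I error shown for bias favouring apixaban:

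| q | g (in SDs of 0.16) | Bias per year | Share of 0.05 | One-sided type I error |
|---|---|---|---|---|
| 2% | 0.5 | 0.0016 | 3% | 5.9% |
| 5% | 0.5 | 0.004 | 8% | 7.6% |
| 10% | 0.5 | 0.008 | 16% | 11.0% |
| 10% | 1.0 | 0.016 | 32% | 21.0% |

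**5. Cost of keeping non-starters.** Assume apixaban non-starters get no benefit, so the effect becomes 0.05 × (1 − q).

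| Apixaban non-start | Power at 140 per arm | Per arm for 80% power |
|---|---|---|
| 2% | about 82% | 132 |
| 5% | 79.9% | 141 |
| 10% | 76.1% | 157 |

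**The case against.** The strongest reply has four parts.

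- **Replacement only adds patients.** A reader might infer that Section 7.2 contradicts Section 9.3. It does not: no sentence removes a replaced patient from the ITT set. This stands, and the defect is an unreconciled silence.
- **Replacement is not what causes the bias.** If non-starters are lost and nobody replaces them, the analysed arm is the same self-selected group, only smaller. This also stands. Deleting the sentence alone would cure nothing; follow-up of non-starters is the part that matters.
- **The documents do not say non-starters go unfollowed.** Section 7.1 opens by asking that remaining procedures be completed after the intervention is stopped. This stands in part. That sentence concerns stopping and does not name patients who never start, and the later withdrawal and censoring wording pulls the other way.
- **Refusal need not fall mainly on warfarin.** A reader might infer that it will, because apixaban is free and "Warfarin and its monitoring will not be paid for by the study since it is considered the standard of care". The documents give no non-start rate or reason. Inclusion criteria 6 and 7 already require willingness to comply with procedures and adhere to the regimen. Prior warfarin exposure is allowed, and a patient already on warfarin and assigned to it has nothing new to start. Excess warfarin refusal is possible but not shown.

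The illustrated bias is also only about 0.2 to 0.4 of a standard error (0.004/0.0191 to 0.008/0.0191). That is fair, and it places the point as an inexpensive safeguard rather than a flaw shown to invalidate the result.

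**Conclusion.** The point holds as a gap. A discretionary replacement rule, usable once allocation is known, is not reconciled with the primary all-randomised analysis, and the plan leaves plausible routes by which a non-starter contributes nothing to that analysis. This is more than missing detail, because the late baseline test and the Section 7.1 censoring rule make the loss likely unless the text prevents it.

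The consequence is conditional. It needs non-starters to be lost, to differ in prognosis from starters, and to differ in number or prognosis between arms. The documents support neither a stated contradiction, nor a known direction, nor a warfarin arm that will certainly be reshaped. The range of 0.004 to 0.008/year is correct arithmetic on assumed rates, and its sign is unknown.

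**What to change.** 1. **Section 7.2:** delete the replacement sentence, or state that any added patient is a new randomisation through the usual stratified list and never a substitute for an earlier one.
2. **Sections 7.2 and 9.3:** state that every randomised patient remains in the ITT set under the assigned arm, is invited to the 1- and 2-year assessments whether or not study drug was started, and that non-starters are reported by arm with reasons.
3. **Section 7.1:** amend the withdrawal and censoring wording to match, so that not starting, or changing anticoagulant, does not by itself end study assessments or remove later scores from the primary ITT analysis. This concerns follow-up and analysis only, not treatment decisions.
4. **Sections 3 and 8.1:** complete baseline cognitive testing and MRI before randomisation. This fits Section 5.4, which already gives dementia found at baseline testing as an example of a screen failure.
5. **Section 9.2:** qualify the power statement for non-start.

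Most of this is wording, plus tighter scheduling of baseline tests and the effort of following patients off study drug. The real cost is dilution: 83.4% power as planned, about 82% at 2% apixaban non-start and about 80% at 5%. If the sponsor expects more, an allowance is needed: 157 per arm at 10%, before any inflation for screen failure or dropout. Non-starters who take the other arm's drug would dilute further. In the assumed 10% and 2% case, the worst-case effect is 0.05 × (1 − 0.10 − 0.02) = 0.044/year.
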